The toxicity profile of irinotecan liposomal injection (ONIVYDE®) with 5-fluorouracil and leucovorin in the second line metastatic setting is very reasonable with the added benefit of improved drug delivery to tumor. In the neoadjuvant setting, where patient toxicity is paramount and tumor vasculature is undisrupted, the incorporation of ONIVYDE® could have an important anti-neoplastic effect by improved biologic drug delivery and improved full treatment compliance. Delivering a complete (4 month) course of systemic therapy with maintenance of patient health and minimization of post-op complications would represent a clinically significant step forward in the field of pancreatic cancer therapy.

[figure not shown]
This protocol aims to substitute irinotecan liposomal injection (ONIVYDE®) for traditional irinotecan in the standard FOLFIRINOX regimen and deliver the therapy in the neoadjuvant setting. The primary goal of this strategy is to rapidly establish perioperative safety with regards to surgical outcomes. The doses and schedule will be those established by the safety run-in/Arm 1 of the currently enrolling randomized phase II front-line study in metastatic pancreatic cancer (NCT02551991). Recent safety data from that study supports the incorporation of ONIVYDE in this combination for previously untreated patients with metastatic pancreatic cancer. This study will also help establish a benchmark for radiographic response rate, pathologic down staging and treatment compliance. Potential post-hoc correlative analyses include, but are not limited to, assessment of pancreatic cancer circulating tumor cells associated with treatment response, development of patient-derived cell lines and xenografts from refractory tumor removed at the time of surgical resection to determine pathways of resistance and microenvironmental immunosuppression, comprehensive mutational profiling of pancreatic adenocarcinoma tissue and pharmacologic precision medicine program assessments of novel pharmacogenomic profiles (e.g., additional haplotypes of UGT1A1, as well as UGT1A7, ABCG2/B1/C2, and SLCO1B1) associated with irinotecan-associated GI toxicity and myelosuppression. Taken together, this study will support continued development of this novel combination regimen in the adjuvant, perioperative or metastatic setting.

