In the phase II NALIRIFOX study (NCT02551991), the MTD (liposomal irinotecan 50 mg/m^2 [free-base equivalent], oxaliplatin 60 mg/m^2, 5-fluorouracil 2400 mg/m^2, leucovorin 400 mg/m^2 every 2 weeks) was based on dose-limiting toxicities and cumulative safety data in four dose-exploration cohorts. The MTD was received by 32 of 56 patients, seven during dose exploration and 25 during dose expansion (median age 58.0 years [range, 39-76], 28 [87.5%] with metastatic disease at diagnosis [29 at study entry], and one receiving study treatment at data cutoff [26 February 2020]). Of these patients, 22 of 32 had grade  $\geq 3$  treatment-related TEAEs, most commonly neutropenia (31.3%), febrile neutropenia (12.5%) and hypokalaemia (12.5%); ten had serious treatment-related TEAEs; and three died from TEAEs considered unrelated to treatment. Median PFS and OS were 9.2 (95% CI: 7.69-11.96) and 12.6 (8.74-18.69) months, respectively.

**NOTE:** nal-IRI dosing according to the prescribing information is expressed as the irinotecan free base. The doses of nal-IRI in publications written before October 2015 were expressed as the irinotecan hydrochloride trihydrate. Converting a dose based on irinotecan hydrochloride trihydrate to a dose based on irinotecan free base is accomplished by substituting the Molecular Weight of irinotecan hydrochloride trihydrate (677.19 g/mole) with the Molecular Weight of irinotecan free base (586.68 g/mole), which results in a conversion factor of 0.866. Therefore, the published expression of the 80 mg/m^2 dose based on irinotecan hydrochloride trihydrate is equivalent to a 69.3 mg/m^2 dose based on irinotecan free base. This was rounded to 70 mg/m^2 to minimize any potential dosing errors. Similarly, the ONIVYDE® monotherapy arm (120 mg/m^2 irinotecan hydrochloride trihydrate) is equivalent to 100 mg/m^2 of irinotecan free base. Information published prior to October 2015 included the background sections of this protocol uses the trihydrate doses (80 mg/m^2 and 120 mg/m^2).

**Table D: Most Common Grade  $\geq 3$  Adverse Events Observed in Nal-IRI Containing Arms Occurring at  $\geq 5\%$  Overall with  $\geq 2\%$  Incidence Versus 5-FU/LV**

Adverse Event, %	Nal-IRI+5-FU/LV (n=117)		Nal-IRI (n=147)		5-FU/LV (n=134)	
	Any Grade	Grades 3/4	Any Grade	Grades 3/4	Any Grade	Grades 3/4

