##### **Neutropenia**

Deaths due to sepsis following severe neutropenia have been reported in patients treated with irinotecan and nal-IRI. Neutropenic complications should be managed promptly with antibiotic support. G-CSF may be used to manage neutropenia at the investigator's discretion or per institutional policy.

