#### 12.6 Enhanced AE Safety Monitoring

When accrual is greater than 10 subjects, if at any time, 5 of the initial 10 treated subjects or 50% or more of all treated subjects have experienced a non-hematologic grade  $\geq$  3,4, 5 adverse event considered at least possibly related to treatment (possible, probable, or

definite), accrual will be temporarily suspended to this study for a review by the PI and the Data Integrity and Safety Committee. Grade 4 and 5 adverse events deemed “unrelated” or “unlikely to be related” will be reviewed and monitored, to assess for the emergence of a previously unrecognized treatment-related adverse event.

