### **13. DATA AND SAFETY MONITORING**

#### **13.1 Data Integrity and Safety Committee**

This protocol will be reviewed and monitored by the University of Florida Health Cancer Center (UFHCC) DISC in accordance with their policies and procedures. They will review and monitor study progress, toxicity, safety and other data from this trial. Questions about subject safety or protocol performance will be addressed with the sponsor-investigator, statistician and study team members. Should any major concerns arise; the DISC will offer recommendations regarding whether or not to suspend the trial.

UFHCC DISC data and safety monitoring activities include:

- Review of clinical trial conducted for progress and safety
- Review of all adverse events requiring expedited reporting as defined in the protocol
- Review of reports generated by data quality control review process
- Notification of the sponsor-investigator of recommended action
- Notification of sites coordinated by the UFHCC of adverse events requiring expedited reporting and subsequent committee recommendations for study modifications

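### Section 12.6 has no automatic accrual pause for deaths: a related death counts the same as a grade 3 event toward a 50% threshold

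*Combined protocol and SAP*

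**What the plan says.** Section 12.6 (Enhanced AE Safety Monitoring) is the only rule in the protocol that ties a count of safety events to an automatic action. It opens "When accrual is greater than 10 subjects, if at any time, 5 of the initial 10 treated subjects" and adds a second limb at half of all treated subjects, so that the condition reads "5 of the initial 10 treated subjects or 50% or more of all treated subjects have experienced a non-hematologic grade" 3, 4 or 5 event. An event qualifies if it is non-hematologic, of grade 3, 4 or 5, and at least possibly related to treatment. The consequence is that "accrual will be temporarily suspended to this study for a review by the PI and the Data Integrity and Safety Committee". The section then says that grade 4 and 5 events judged unrelated or unlikely to be related are reviewed and monitored. No count or pause is attached to that review.

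Other sections bear on the point:

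- Section 1.2: "The primary goal of this strategy is to rapidly establish perioperative safety with regards to surgical outcomes".
- Section 1.4.2 reports, at the dose used here, grade 3 or higher treatment-related neutropenia in 31.3% of patients and febrile neutropenia in 12.5%.
- Section 10.1.8, under Neutropenia: "Deaths due to sepsis following severe neutropenia have been reported in patients treated with irinotecan and nal-IRI".
- Section 11.3.1 rates causality against study medication only.
- Section 12.2 makes death within 30 days of surgery a component of the primary endpoint.
- Section 8.2 has deaths during the trial, or within 30 days of stopping treatment, reported to the DISC. Section 11.4.1 has serious adverse events reported to its safety team within 5 days.
- Section 13.1: "Should any major concerns arise; the DISC will offer recommendations regarding whether or not to suspend the trial".

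**The concern.** A rule that pools grades 3 to 5 at one 50% threshold is set for the frequency of ordinary severe toxicity. Fatal toxicity would cause alarm at a far lower frequency, yet the rule gives it no extra weight. The excluded hematologic category is also one that the protocol itself links to deaths.

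The patients have resectable or borderline resectable disease and are treated with curative intent, and perioperative safety is the stated goal. An excess of treatment-related deaths could build up while the automatic rule stays silent. Whether accrual then paused would depend on judgment, with no count agreed beforehand.

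**Working it through.** Section 12.6 states no target rate, error rate or trigger probability, so there is no figure of the plan's own to reproduce. The inputs are its thresholds (5 of the first 10, or at least 50% of all treated), its start after 10 accrued, and the planned 28 subjects (section 12.1). All true rates below are assumptions, shown as a range.

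**1. Direct count.** Four related deaths in the first ten are 4/10 = 40%, below the first limb. At 11 treated, the second limb needs 6. Counting deaths alone, as many as 5 of 11, 9 of 20 or 13 of 28 stay under 50%, provided that no more than 4 fall in the first ten.

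**2. The condition on that example.** One qualifying event in any of the other six subjects makes 5/10 and trips the rule. If each of the six has probability q of such an event, P(trip) = 1 − (1 − q)^6:

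| q | P(trip) |
|---|---|
| 0.1 | 47% |
| 0.2 | 74% |
| 0.3 | 88% |
| 0.4 | 95% |

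The documents give no rate for non-hematologic events alone, so q is assumed.

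**3. The full rule from deaths alone.** Let X_n be the number of qualifying subjects among the first n, with independent probability p each. The rule trips if X_10 ≥ 5, or if X_n ≥ n/2 for some n from 11 to 28.

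| True rate p | First-ten limb | Any trip by n = 28 |
|---|---|---|
| 10% | 0.2% | 0.2% |
| 20% | 3.3% | 3.9% |

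**4. The full rule with background toxicity.** Suppose each subject also has an independent chance b of a qualifying grade 3-4 event. With death rate d, p = 1 − (1 − d)(1 − b).

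| d | b | p | Any trip by n = 28 |
|---|---|---|---|
| 10% | 20% | 1 − 0.9 × 0.8 = 0.28 | 15% |
| 10% | 30% | 1 − 0.9 × 0.7 = 0.37 | 40% |
| 20% | 20% | 1 − 0.8 × 0.8 = 0.36 | 36% |
| 20% | 30% | 1 − 0.8 × 0.7 = 0.44 | 63% |

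With no deaths at all, the rule trips with probability 3.9% at b = 20% and about 20% at b = 30%. A trip is therefore not specific to deaths.

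**5. A trigger at the second related death.** For n = 28, P(≥ 2) = 1 − (1 − p)^28 − 28p(1 − p)^27.

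| p | Calculation | P(fires) |
|---|---|---|
| 2% | 1 − 0.568 − 0.325 | 11% |
| 5% | 1 − 0.238 − 0.350 | 41% |
| 10% | 1 − 0.052 − 0.163 | 78% |
| 20% | 1 − 0.002 − 0.014 | 98% |

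**6. Two further triggers that might be considered.**

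- *Third death within 30 days of surgery.* Section 1.1 quotes post-operative mortality of 3.8-7.5%. With 28 operated, P(≥ 3) is 8.9% at 3.8% and 35.1% at 7.5%, so the risk of a false pause is about 9-35%.
- *Complication looks at 10 and 20 operated subjects.* Eight two-weekly cycles put the last dose at week 14. Surgery follows 4-8 weeks later, and the endpoint needs 30 more days, so each outcome takes about 5.1-6.0 months. Accrual of 28 in 20 months is 1.4 per month, so the 20th subject enters at 20/1.4 = 14.3 months and has an outcome at about 19.4-20.3 months. If 10% are not operated, 20/0.9 = 22.2 subjects are needed, and the look falls at about 21-22 months. Accrual is by then essentially complete. Only the 10-subject look could act. At 6 or more of 10, it fires with probability 4.7%, 38% and 63% at complication rates of 30%, 50% and 60%.

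**The case against.** The strongest reply is that only an automatic pause is missing, since detection and review are already provided for. Deaths and serious events go to the DISC, reviewing expedited events is one of its listed duties, and it may recommend suspension. Section 12.6 itself reviews grade 4 and 5 events judged unrelated. A tripped rule leads only to a pause for review by the same people. All of this stands and limits the point. What it does not supply is a count agreed beforehand at which accrual stops while deaths are examined. The plan saw a need for such a count for pooled grade 3-5 events.

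A reader might infer more than the documents support in four ways:

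- *That post-operative events are excluded.* Section 12.6 has no time window and no such exclusion. A non-hematologic post-operative event rated at least possibly related does count. Events drop out by attribution: under section 11.3.1, a competing cause such as surgery points away from a related rating.
- *That four toxic deaths in ten could not pause accrual.* This holds only for the automatic rule, and only if the other six subjects have no qualifying event. Section 1.4.2 reports 22 of 32 patients with grade 3 or higher related events at this dose, hematologic events included, so no background toxicity at all is unlikely.
- *That the rule cannot detect excess fatal toxicity.* Step 4 shows that it may trip, although largely through the accompanying grade 3-4 events.
- *That neutropenic sepsis deaths are certainly excluded.* Section 12.6 does not define non-hematologic. The footnote to Table D groups neutropenic sepsis with neutropenia, while the table in section 7.3.3 covers only neutrophil and platelet toxicity. The classification is open.

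**Conclusion.** The point holds as a gap in the automatic rule. Section 12.6 attaches no pause to deaths as such, and it is very insensitive to them: 0.2% at a 10% related-death rate and 3.9% at 20%, over 28 subjects and from deaths alone. Related hematologic deaths and post-operative deaths judged unrelated to treatment rest on DISC review and its discretionary recommendation. The plan is not without safety oversight.

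The figures assume independent subjects, a constant rate and 28 treated. Subjects who do not reach surgery are replaced (section 8.3), so more than 28 may be treated, which would raise every trigger probability somewhat. The probabilities for the second-death trigger include a second death after the last enrollment, which would prompt review but leave no accrual to suspend. The documents give no acceptable rate of toxic death, so the 2% reference is an assumption.

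The case for a related-death trigger does not extend with equal force to post-operative deaths or primary-endpoint complications. At the protocol's own background mortality, a third-death trigger would often pause the trial needlessly, and a 20-patient complication look would come too late to affect accrual.

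**What to change.** Add one limb to section 12.6: accrual is temporarily suspended for review by the PI and the DISC at the second grade 5 event at least possibly related to treatment, hematologic causes included, whatever the number accrued. State its operating characteristics from step 5 beside it, with the assumptions.

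The cost is one paragraph, using data that the DISC already receives, and about an 11% chance of an unneeded short pause if the true toxic-death rate is 2%.

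Triggers for post-operative deaths or primary-endpoint complications are optional. If the sponsor and the DISC want them, they should calibrate them to the quoted surgical mortality and to the accrual timeline, and report both false-pause and detection probabilities.

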### **13. DATA AND SAFETY MONITORING**

#### **13.1 Data Integrity and Safety Committee**

This protocol will be reviewed and monitored by the University of Florida Health Cancer Center (UFHCC) DISC in accordance with their policies and procedures. They will review and monitor study progress, toxicity, safety and other data from this trial. Questions about subject safety or protocol performance will be addressed with the sponsor-investigator, statistician and study team members. Should any major concerns arise; the DISC will offer recommendations regarding whether or not to suspend the trial.

UFHCC DISC data and safety monitoring activities include:

- Review of clinical trial conducted for progress and safety
- Review of all adverse events requiring expedited reporting as defined in the protocol
- Review of reports generated by data quality control review process
- Notification of the sponsor-investigator of recommended action
- Notification of sites coordinated by the UFHCC of adverse events requiring expedited reporting and subsequent committee recommendations for study modifications

#### **13.2 Monitoring**

UFHCC monitors will utilize on-site and/or remote monitoring periodically during the trial to determine whether sites are complying with the protocol. Source documents will be reviewed for verification of agreement with data as submitted via the data collection system. The site investigator/institution guarantee access to source documents by UFHCC or its designee and appropriate regulatory agencies.

The trial site may also be subject to quality assurance audit by any collaborating sponsors or their designee as well as inspection by appropriate regulatory agencies.

It is important for the site investigator and their relevant personnel to be available during the monitoring visits and possible audits and for sufficient time to be devoted to the process.

#### **13.3 Principal Investigator Responsibilities**

As part of the responsibilities assumed by conducting this study, the Principal Investigator (PI) agrees to maintain and have available for monitoring adequate case records (accurate source documents and CRFs) for the subjects treated under this protocol.

The PI will be primarily responsible for monitoring of adverse events, protocol violations, and other immediate protocol issues. The study coordinator will collect information on subjects

enrolled through the use of electronic or paper adverse event (AE) forms, CRFs, and Informed Consent forms.

## **14. EMERGENCY PROCEDURES**

### **14.1 Emergency Contact**

In emergency situations, the treating physician should contact the Principal Investigator by telephone at the number listed on the title page of the protocol.

### **14.2 Emergency Identification of Investigational Products**

This is a non-blinded, non-randomized study. Thus, there will be no need for unmasking procedures, and the identification of the investigational product can be made by simple inquiry to the investigational pharmacy.

### **14.3 Emergency Treatment**

During and following a subject's participation in the study, the treating physician and/or institution should ensure that adequate medical care is provided to a subject for any adverse events, including clinically significant laboratory values, related to the study.

## **15. ADMINISTRATIVE, ETHICAL, AND REGULATORY CONSIDERATIONS**

### **15.1 Good Clinical Practice**

The procedures set out in this study protocol pertaining to the conduct, evaluation, and documentation of this study are designed to ensure that the Principal Investigator and Co-Investigators abide by Good Clinical Practice (GCP), as described in International Conference on Harmonization (ICH) Guideline E6 and in accordance with the general ethical principles outlined in the Declaration of Helsinki.

The study will be conducted in compliance with the protocol. The protocol, any amendments, and the subject informed consent will receive Institutional Review Board (IRB) approval before initiation of the study.

The Principal Investigator will conduct all aspects of this study in accordance with applicable national, state, and local laws of the pertinent regulatory authorities.

All potential serious breaches must be reported immediately to the UFHCC DISC and IRB of record, if applicable. A serious breach is a breach of the conditions and principles of GCP in connection with the study or the protocol, which is likely to affect, to a significant degree, the safety or physical or mental integrity of the subjects of the study or the scientific value of the study.

## 15.2 Institutional Review Board

Before study initiation, the investigator must have written and dated approval from the IRB for the protocol, consent form, subject recruitment materials/process (e.g., advertisements), and any other written information to be provided to subjects. The investigator should also provide the IRB with a copy of the Investigator Brochure or product labeling, information to be provided to subjects, and any updates. The investigator should provide the IRB with reports, updates, and other information (e.g., amendments, and administrative letters) according to regulatory requirements or institution procedures.

## 15.3 Delegation of Investigator Responsibilities

The Principal Investigator will ensure that all persons assisting with the study are adequately informed about the protocol, any amendments to the protocol, the study treatments, and their study-related duties and functions. The Principal Investigator will maintain a list of Co-Investigators and other appropriately qualified persons to whom he has delegated significant study-related duties.

Study personnel involved in conducting this study will be qualified by education, training, and experience to perform their respective tasks. This study will not use the services of study personnel where sanctions have been invoked or where there has been scientific misconduct or fraud (e.g., loss of medical licensure; debarment). Systems with procedures that ensure the quality of every aspect of the study will be implemented.

## 15.4 Subject Information and Informed Consent

Before being enrolled in this clinical trial, the subject must consent to participate after the nature, scope, and possible consequences of the clinical study have been explained in a form understandable to him or her. An informed consent document that includes both information about the study and the consent form will be prepared and given to the subject. This document will contain all ICH, GCP, and locally required regulatory elements. The document must be in a language understandable to the subject and must specify the person who obtained informed consent.

After reading the informed consent document, the subject must give consent in writing. The written informed consent will be obtained prior to conducting any study-related procedures or tests. The subject's consent must be confirmed at the time of consent by the personally dated signature of the person conducting the informed consent discussions. A copy of the signed consent document must be given to the subject.

The PI will retain the original signed consent document. The PI will not undertake any measures specifically required only for the clinical study until valid consent has been obtained.

## 15.5 Confidentiality

---

All records identifying the subject will be kept confidential and, to the extent permitted by the applicable laws and/or regulations, will not be made publicly available.

Should direct access to medical records require a waiver or authorization separate from the subject's statement of informed consent, it is the responsibility of the Investigator to obtain such permission in writing from the appropriate individual.

Subjects will be told that the IRB, UF Health DISC, or regulatory authorities may inspect their medical records to verify the information collected, and that all personal information made available for inspection will be handled in strictest confidence and in accordance with local data protection law.

